8.2 Serious Adverse Events

Definition

An adverse event is reported as a 'Serious Adverse Event' if it meets any of the following criteria [as per International Conference on Harmonisation (ICH) Good Clinical Practice (GCP) Guidelines]:

- results in death
- is life threatening
- results in persistent or significant disability/incapacity
- requires in-participant hospitalization or prolongs existing hospitalization
- is a congenital anomaly/ birth defect
- any other important medical condition that requires medical or surgical intervention to prevent permanent impairment of a body function or structure. An elective surgery for a pre-existing condition that did not increase in severity or frequency is not considered an SAE.

8.3 Reporting adverse events of special interest (AESIs)

Potential immune-mediated diseases

Potential immune-mediated diseases are a subset of AEs that include both clearly autoimmune diseases and other inflammatory and/or neurologic disorders that may or may not have an autoimmune aetiology. These events are of special interest since they could potentially be caused by immune responses to the study product. The investigator/designee should report such AEs within the

same time limits and using the same CRF pages, as utilized for SAEs. The investigator or his/her designee will evaluate the occurrence of AESIs at every visit/contact during the study. AEs to be reported and documented as AESIs include:

- Neuroinflammatory disorders: optic neuritis, cranial nerve disorders (including Bell's palsy), multiple sclerosis, demyelinating disease, transverse myelitis, Guillain-Barré Syndrome, myasthenia gravis, encephalitis, neuritis.
- Musculoskeletal disorders: systemic lupus erythematosus, cutaneous lupus, Sjögren's syndrome, scleroderma, dermatomyositis, polymyositis, myopathy, rheumatoid arthritis and juvenile rheumatoid arthritis, polymyalgia rheumatica or temporal arteritis, reactive arthritis, psoriatic arthropathy, ankylosing spondylitis, undifferentiated spondyloarthropathy.
- Gastrointestinal disorders: Crohn's disease, ulcerative colitis or proctitis, celiac disease.
- Metabolic diseases: autoimmune thyroiditis, Grave's or Basedow's disease, Hashimoto thyroiditis, insulin-dependent diabetes mellitus, Addison's disease.
- Skin disorders: psoriasis, vitiligo, Raynaud's phenomenon, erythema nodosum, autoimmune bullous skin diseases.
- Others: autoimmune haemolytic anaemia, thrombocytopenia, antiphospholipid syndrome, *vasculitis, pernicious anaemia, autoimmune hepatitis, primary biliary cirrhosis, primary sclerosing cholangitis, autoimmune glomerulonephritis, autoimmune uveitis, autoimmune myocarditis/cardiomyopathy, sarcoidosis, Stevens-Johnson syndrome, Behçet's syndrome.
- Injection/infusion site reactions: Grade 3 or 4 injection/infusion site reactions lasting more than 2 days.
- Vasculitis: Vasculitis, Diffuse vasculitis, leucocytoclastic vasculitis, polyarteritis nodosa, microscopic polyangiitis, Wegener's granulomatosis, anti-neutrophil cytoplasmic antibody positive vasculitis, Henoch-schönlein purpura, allergic granulomatous angiitis (Churg- Strauss disease), Kawasaki disease, Takayasu's arteritis, temporal arteritis (giant cell arteritis), renal vasculitis.

Medical judgement should be exercised in deciding whether other disorders/diseases have an autoimmune origin and should also be reported as described above, and this judgement is the investigator's prerogative. Whenever sufficient data exist to substantiate any of the diagnoses in the above list, the event must be reported as an AESIs. While the intent of AESIs reporting is to be inclusive, isolated nonspecific symptoms, which might (or might not) represent the above diagnoses, should be captured as AEs but not reported as AESIs until the diagnosis can be defended.

8.4 Discontinuation of study product/s administration

Participants will be withdrawn from study product use for any of the reasons listed below. These participants will not receive any additional dose of study product but will continue safety follow-up as per SSP.

- Pregnancy
- Immediate hypersensitivity reaction associated with the study product
- Any grade 4 reactogenicity event that is assessed as related to the study product
- Any grade 3 or higher adverse event that is assessed as related to the study product
- An SAE that is subsequently considered to be related to study product
- Intercurrent illness that is not expected to resolve prior to the next scheduled study product administration, which is assessed by the PI (or designee) to require withdrawal from the product administration
- Repeated failure to comply with protocol requirements
- Co-enrolment into another study that in the opinion of the PI may interfere with the study objectives and participant safety
- The study PI decides to stop or cancel the study.
- The regulatory authorities halt the study.

8.5 Clinical management and Reporting of Adverse Events

Adverse events will be managed by the clinical study team, who will assess, provide first line of care as appropriate and refer to health care and treatment facilities as warranted. Participants will be followed until the AE resolves or stabilizes. If at study exit, an AE (including clinically significant laboratory abnormality) that is considered related to the study product is unresolved, follow-up will continue until resolution, if possible, and/or the participant will be referred for further management. All AEs will be reviewed regularly by the Protocol Safety Review Team (PSRT).

8.6 Safety monitoring

Safety monitoring includes internal monitoring by the study team, the protocol safety review team, data safety monitoring board and/or audits.

Internal monitoring

Safety reporting of SAEs, AEs and other important reportable events will be the responsibility of the entire study team. In addition, the study statistician will prepare routine study safety progress reports which include reports of AEs experienced by study participants (blinded to treatment assignment) for review by the PSRT. The PSRT will be responsible for decisions related to participant safety.

Protocol safety review team (PSRT)

A PSRT will be formed to monitor the clinical safety data. The membership, scope of responsibility, role and modus operandi of the PSRT will be defined in the SOP. The PSRT will review the clinical safety data on a regular basis via electronic distribution of reports and will have face-to face meetings as required. Events identified as questionable, inconsistent, or unexplained will be queried for verification. Any deaths of study participants or other SAEs will be reviewed, and a decision taken by the PSRT on whether pause rules have been met and whether a Data Safety Monitoring Board (DSMB) review is warranted. An *ad hoc* PSRT review meeting will occur if any of the members of the PSRT requests a special review to discuss a specific safety issue or as specified in the SOP.

Data safety monitoring board (DSMB)

In addition to monitoring performed by the PSRT, an independent DSMB will review the study data. Details for the operation and responsibilities of the DSMB will be defined in the DSMB Charter and SOP, which will delineate the composition, duties, responsibilities and procedures of the DSMB, data required at each meeting, as well as the analyses that will be conducted.

The DSMB will meet in-person and/or via teleconference at least twice a year. More frequent or *ad hoc* reviews of safety reports may be conducted by the DSMB as needed. The DSMB could recommend that the study should proceed as designed, should proceed with design modifications, or should be discontinued.

Monitoring

The PI will permit authorized representatives to inspect the site facilities and records relevant to the study. A detailed monitoring plan will be developed prior to the start of the study. The monitor will ensure that any compliance issues are addressed with the PI/designee and study team and will report to the relevant authorities as required.

9.0 STATISTICAL CONSIDERATIONS PART A

9.1 Accrual, sample size and follow-up

Based on the preliminary data from the phase 1 CAPRISA studies that evaluated CAP256V2LS and VRC07-523LS, we assume that 6% of participants in the intervention arm will experience at least one local or systemic grade 3 or higher reactogenicity events within the first 3 days after administration of CAP256V2LS and VRC07-523LS. There were no grade 3 or higher reactogenicity events reported in the participants who received placebo injections; however, these projects were not large enough to

be able to detect rare events. As this is preliminary data, we therefore assume that 1% to approximately 1.5% of participants receiving placebo will experience local or systemic grade 3 or higher reactogenicity events within the first 3 days after administration. A sample size of 984 will provide 90% power to detect a minimum 4-fold higher rate of an event on an assumption of 1.5% rate in the placebo receiving participants. These calculations were based on a Fisher's exact with a 2- sides type I error rate of 0.05. We assume a dropout rate of 5%. **Table 3** provides the sample size for different estimates.

Table 3: Number of participants to have 90% power to detect a safety event

Scenario	1	2	3	4	5	6	7
Event rate in the intervention arms	7.0%	7.0%	7.0%	6.0%	6.0%	6%	6.0%
Event rate in the control arm	0.5%	1.0%	2.0%	0.5%	1.0%	1.5%	2.0%
Sample size: combined intervention arms (1:1)	296	360	464	336	464	656	844
Sample size: control arm	148	180	232	168	232	328	422

However, based on the rationale provided in section 2.6.2, the trial design was amended and sample size of 984 was reduced to 90. The sample size justification for part B can be found in section 9.2.

PART B

9.2 Accrual, sample size and follow-up

Based on the preliminary data from the phase 1 CAPRISA studies that evaluated CAP256V2LS and VRC07-523LS, and the fact that a fixed dose of study product will be used in part B. The fixed dose is expected to be associated with fewer grade 3 or higher reactogenicity events than the weight-based dose. We assume that 4.8% of participants in the intervention arm compared to 1% in the control arm, will experience at least one local or systemic grade 3 or higher reactogenicity events within the first 3 days after administration of CAP256V2LS and VRC07-523LS.

A sample size of 900 will provide 90% power to detect a minimum 4.8-fold higher rate of an event. These calculations were based on a Fisher's exact with a 2- sides type I error rate of 0.05. Given a longer interval between study visits, we assume a dropout rate of 10% which has been incorporated into the total sample size. **Table 4** provides the sample size for different estimates.

Table 4: Number of participants to have 90% power to detect a safety event

Scenario	1	2	3	4
Event rate in the intervention arms	6.0%	6.0%	5.0%	4.8%
Event rate in the control arm	1.0%	1.5%	1.0%	1.0%
Sample size per arm	300	400	423	450
Total sample size	600	800	846	900

The goal of this study is to identify safety concerns associated with the product. The ability of the study to detect rare events is shown in **Table 5**. This was done by calculating the probability of detecting no events, at least one or at least two events at a specified true event rate. These probabilities highlight the likelihood of the study to detect either rare or common grade 3 or higher reactogenicity events or even serious adverse events. Also, the 95% confidence interval for the true event rate was calculated in **Table 6** using the score test method (42). For the 450 participants who will receive CAP256V2LS + VRC07-523LS, there is a 10% chance of observing no events if the true event rate is 0.5%, but there is a very low probability of detecting no events when the event rate is 2% or higher. The chance of observing at least one event is $\geq 90\%$ if the true event rate is 0.5% or more.

Table 5: Probability of observing no events, at least 1 event, or at least 2 events, for a range of hypothetical true event rates (N=450).

True event rate (%)	0 events	1+ events	2+ events
0.5	0.1	0.90	0.48
1	0.01	0.99	0.94
2	<0.001	>0.99	>0.99
4.8	<0.001	>0.99	>0.99
6	<0.001	>0.99	>0.99
10	<0.001	>0.99	>0.99

Table 5 shows the two-sided exact 95% confidence interval for the observed true event rate. If one or two of the 450 participants receiving CAP256V2LS and VRC07-523LS experiences a safety event, the upper bound of the two-sided 95% confidence interval will be 1.25% or 1.61%, respectively. If 20 or 40 participants experienced an event, these estimates of 4.4% and 8.9% will be compatible with plausible event rates from 2.90% to 6.76% and 6.60% to 11.88%, respectively.

Table 6: Two-sided 95% confidence intervals based on observing a particular rate of safety endpoints

Number of events/ sample size	95% confidence interval
0/450	0 – 0.85
1/450	0.04 – 1.25
2/450	0.12 - 1.61
10/450	1.21 – 4.04
20/450	2.90 – 6.76
40/450	6.60 – 11.88

Since this extended safety study is being undertaken in the populations where a phase III trial would be conducted, it is expected to generate a preliminary estimate of efficacy. The statistical power to demonstrate 67% efficacy is 82% if the background incidence rate in the phase II trial is 4 per 100 person-years and 90% if the HIV incidence rate is 5 per 100 person-years. The rationale for using the background HIV incidence rate ranging from 3 to 5 per 100 person-years, is that the HIV incidence rate in the placebo arm of the AMP, ASPIRE and RING study were 2.98, 4.5 and 6.1 per 100 women-years, respectively. The calculations in **Table 7** allows for a lower HIV incidence in Zambia. Power calculations were based on an exponential maximum likelihood test of equality of survival curves from nQuery (2021) (Statistical Solutions Ltd), Cork, Ireland.

Table 7: Power and HIV endpoints for varying effectiveness and background incidence rate

Statistical power for background HIV incidence rates when the sample size is 900; accrual of 9-12 months and maximum follow-up of 24 months				
Incidence	67% effectiveness		80% effectiveness	
	HIV events	Power	HIV events	Power
2	13	53%	9	67%
3	20	70%	13	84%
4	27	82%	18	93%

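### Table 5 gives 0.48 as the chance of seeing two or more events at a true rate of 0.5% with 450 women; the binomial value is 0.66

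*Protocol*

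**What the plan says.** All of this stands in protocol section 9.2 (Part B).

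- The calculation behind Table 5 is defined in words: "This was done by calculating the probability of detecting no events, at least one or at least two events at a specified true event rate". The caption fixes the sample size: "Probability of observing no events, at least 1 event, or at least 2 events, for a range of hypothetical true event rates (N=450".
- The row for a true rate of 0.5% reads "0.5 0.1 0.90 0.48" (rate in %, then no events, at least one, at least two). The row for 1% reads "1 0.01 0.99 0.94". From 2% upwards the entries are below 0.001 for no events and above 0.99 for the other two columns.
- The text repeats the zero-event figure: "For the 450 participants who will receive CAP256V2LS + VRC07-523LS, there is a 10% chance of observing no events if the true event rate is 0.5" percent. It also puts the chance of at least one event at 90% or more from that rate upwards. It does not repeat the 0.48.
- Before the tables, the text says that the Table 6 intervals were obtained "using the score test method (42"). After Table 5 it says "Table 5 shows the two-sided exact 95% confidence interval for the observed true event rate", and then discusses values that are printed in Table 6. The caption of Table 6 names no method: "Two-sided 95% confidence intervals based on observing a particular rate of safety endpoints".

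**The concern.** The three probabilities in a row of Table 5 are tied together. The chance of at least two events is the chance of at least one, less the chance of exactly one. In the 0.5% row the printed figures imply a chance of exactly one event of 0.90 − 0.48 = 0.42, which is implausibly high when 450 × 0.005 = 2.25 events are expected.

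The 0.5% row is also the informative one. At 1% and above, the chance of seeing two or more events is already at least 0.94. At 0.5% a reader is told that two or more events are slightly less likely than not. Section 9.2 states that the study exists to identify safety concerns and points to this table for rare events, including serious adverse events, so the figure describes a stated property of the design.

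The sentence after Table 5 is a lesser matter. It names the wrong table and a different interval method from the one given shortly before.

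**Working it through.** **Inputs.** n = 450 (antibody arm, Table 5 caption and text); true rates p from Table 5; number of events X distributed Binomial(n, p).

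**Formulas.**
P(0) = (1 − p)^n
P(exactly 1) = n·p·(1 − p)^(n − 1)
P(at least 1) = 1 − P(0)
P(at least 2) = 1 − P(0) − P(exactly 1)

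**Check row, p = 1%.** P(0) = 0.99^450 = 0.0109. P(exactly 1) = 4.5 × 0.99^449 = 0.0494. P(at least 1) = 0.9891. P(at least 2) = 0.9398. The table prints 0.01, 0.99 and 0.94, so the formulas and n = 450 are those the table uses. At 2% the values are 0.0001, 0.9999 and 0.9989, which also agree, as do the rows above 2%.

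**Row in question, p = 0.5%.**

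| Quantity | Calculation | Result | Table 5 |
|---|---|---|---|
| P(0) | 0.995^450 | 0.1048 | 0.1 |
| P(at least 1) | 1 − 0.1048 | 0.8952 | 0.90 |
| P(exactly 1) | 2.25 × 0.995^449 | 0.2370 | not shown |
| P(at least 2) | 1 − 0.1048 − 0.2370 | 0.6582 | 0.48 |

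The difference is 0.66 − 0.48 = 0.18.

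**Internal consistency.** For n = 450, P(exactly 1) is largest at p = 1/450, where it equals (449/450)^449 = 0.368. The 0.42 implied by the printed row exceeds that maximum, so no true rate with 450 women could give 0.90 and 0.48 together.

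**Could another convention give 0.48?**
- Poisson with mean 2.25: 0.6575.
- Normal approximation: 0.69 with continuity correction, 0.57 without.
- At least three events instead of at least two: 0.39.
- 10% dropout, n = 450 × 0.9 = 405: 0.60.
- A smaller n: 0.48 needs about 320 to 325 women. P(0) would then be about 0.20, and the chance of two or more events at 1% would be 0.83 to 0.84. The table prints 0.1 and 0.94.

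None of these fits.

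**Intervals in Table 6.** Score (Wilson) interval with p̂ = x/n and z = 1.96: [p̂ + z²/(2n) ± z·√(p̂(1 − p̂)/n + z²/(4n²))] / (1 + z²/n). For 1/450 this is (0.00649 ± 0.00609)/1.00854, that is 0.04% to 1.25%.

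| Events/450 | Table 6 (%) | Score (%) | Exact, Clopper-Pearson (%) |
|---|---|---|---|
| 0 | 0–0.85 | 0–0.85 | 0–0.82 |
| 1 | 0.04–1.25 | 0.04–1.25 | 0.01–1.23 |
| 2 | 0.12–1.61 | 0.12–1.61 | 0.05–1.60 |
| 10 | 1.21–4.04 | 1.21–4.04 | 1.07–4.05 |
| 20 | 2.90–6.76 | 2.90–6.76 | 2.74–6.78 |
| 40 | 6.60–11.88 | 6.60–11.88 | 6.43–11.91 |

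All six printed intervals are score intervals. The exact ones differ in every row, by at most 0.03 percentage points at the upper limit and 0.17 at the lower.

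**The case against.** The best defence is that nothing in the protocol turns on this cell. The 900 comes from a two-arm Fisher's exact calculation of 4.8% against 1% (Table 4), and section 9.4.2 compares reactogenicity with Fisher's exact test. The safety oversight in section 8.6 does not refer to Table 5. The text below the tables uses only the zero-event and at-least-one figures, which reproduce to rounding (0.895 is printed as 0.90). The error is also conservative, since the trial can see more than the table claims. All of this stands. It limits the weight of the point but does not make the cell right.

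On the intervals, the defence largely succeeds. Section 9.2 names the score method and places the intervals in Table 6, and the printed values agree with that. Only the later sentence is wrong, in its table number and in the word *exact*.

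Three stronger inferences are tempting, and the documents do not support them:

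- A reader might infer that 0.48 is left over from a calculation with a smaller arm. The neighbouring cells contradict an n of about 323, and no arm of 320 to 325 appears in the protocol. The nearest, 328 in Table 3, gives 0.49. The origin cannot be established.
- A reader might infer from *exact* that the lower limits in Table 6 are misstated. They are correct for the method declared before the tables.
- A reader might infer that the protocol must commit to score intervals in the analysis. Tables 5 and 6 are planning illustrations, and the choice of interval for the results can be left to the statistical analysis plan.

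**Conclusion.** One cell of Table 5 is wrong: at a true rate of 0.5% with 450 women, the probability of two or more events is 0.66, not 0.48. The chance is therefore about two in three where the table says slightly under one in two. This rests only on the binomial model with independent women, a common event rate and all 450 counted, which is the model that reproduces every other cell. The error understates the trial's ability to detect rare events. It leaves the sample size of 900, the Fisher's exact test and the values in Table 6 unchanged.

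The sentence that assigns exact intervals to Table 5 is a minor wording slip: wrong table number, wrong method name, correct numbers.

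**What to change.** In Table 5, row 0.5%, last column, replace 0.48 with 0.66. In the sentence that opens the paragraph after Table 5, refer to Table 6 and describe the intervals as two-sided 95% score intervals, in line with the method named earlier in section 9.2. The cost is one cell and one sentence. No recalculation of sample size or power and no change to the design or the planned analysis follows, and the corrected figure is more favourable to the trial.

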9.3 Randomisation and arm allocation

In part A, participants will be randomised in a 2:1:2:1 ratio to receive the following: CAP256V2LS and VRC07- 523LS antibodies administered SC every 16 weeks or placebo; CAP256V2LS and VRC07- 523LS antibodies administered SC every 24 weeks or placebo. Whereas in part B, participants will be randomised in a 1:1 ratio to receive a fixed dose of CAP256V2LS and VRC07- 523LS antibodies administered SC every 24 weeks (6 monthly) or placebo.

Participants and study staff (except for study pharmacists) will be blinded as to participant treatment and initially will also be blinded to treatment schedule (where applicable). The randomization list containing, unique sequential treatment codes, will be generated by an unblinded study statistician and will be used to assign individual study participants to one of the two study arms within a 4- and 6-monthly dosing schedule. The randomization list will be obtained by computer generated random numbers, where a randomly permuted block design, stratified by research site, will be used. The site study pharmacist at each research site is responsible for secure storage of this list. A separate blinded list consisting only of the blinded treatment code, in sequential order, will be provided to the study clinic. Alternatively, this blinded list will be provided through DFdiscover system.

All the unblinding decisions will be made by the principal investigator, where possible, after consultation with the DSMB or the PSRT.

9.4 Statistical analyses

9.4.1 Study populations

Modified intention to treat population (MITT)

This population includes all randomized participants. Those who will be identified as ineligible for enrolment based on pre-randomization criteria and also those who will be randomized but not enrolled (i.e., do not receive the first dose of the injection) and therefore do not contribute data post randomisation will be excluded.

Safety population

The safety population should in essence be the same as the MITT population because participants who do not receive the study product after randomisation are excluded.

9.4.2 Data analyses

Analyses for primary endpoint(s) and some of the secondary endpoints will be performed using SAS version 9.4 or above (Statistical Analysis Software, North Carolina, USA) and or R statistical software. MITT analyses will be used for the analyses of safety endpoints. Inferential statistical analyses will be performed with all participants receiving CAP256V2LS and VRC07-523LS antibodies irrespective of the dosing frequency (in Part A) grouped and compared to all the participants receiving placebo. Sensitivity analyses may be performed where the intervention arm will be compared to the placebo arm within each dosing frequency (in Part A).

All deviations to be made to the statistical considerations in this protocol will be documented in the detailed statistical analyses plan (SAP) together with a detailed analysis plan for secondary objectives.

Participant demographics

Demographic data of all participants enrolled in the study will be summarized using descriptive statistics. No inferential statistics will be performed to compare demographics and any other baseline variables by study arm.

Reactogenicity

The number and percentage of participants experiencing each type of reactogenicity sign or symptom will be tabulated by severity and study arm. Each participant's reactogenicity sign or symptom will be counted once under the maximum severity for each injection. In the combined intervention and controls arms, the number and proportion of participants experiencing at least one grade 3 or higher local or systemic reactogenicity signs and symptoms across all injection visits will be compared using Fisher's exact test.

Adverse events and serious adverse events

Medical Dictionary for Regulatory Activities (MedDRA) will be used to summarise all AEs and SAEs events by system organ class (SOC) and preferred terms for each of the study arms. Moreover, the number and percentages of participants experiencing each specific AE within each of the SOC and preferred term will be tabulated by severity and relationship to study product. The timing of the adverse events with respect to the injection will be reported. For the calculations in these tables, each participant's adverse experience will be counted once under the maximum severity or strongest recorded causal relationship to study product. However, all grade 3 or higher adverse events deemed related to the study product will be summarised separately. A separate listing of all SAEs will be reported.

Local laboratory values

For each local laboratory measure, summary statistics will be presented by the treatment arm at each time point where is measured. In addition, the number and percentage of participants with local gradable laboratory values recorded will be tabulated by study arm for each post-vaccination time point. Reportable clinical laboratory abnormalities without an associated clinical diagnosis will also be included in the tabulation of AEs described above. For ease of reference, selected laboratory tests will be presented graphically and where appropriate, horizontal lines representing the laboratory reference for the upper and lower bound values will be plotted.

bnAbs concentrations in the genital tract

Boxplots and descriptive statistics will be used to summarize bnAbs concentrations over time. Depending on the distribution of bnAbs concentrations, we will build a longitudinal model (either use mixed effects models or generalised estimating equations) and adjust for variables that are potentially correlated with bnAbs concentrations.

HIV infections

This sub-section is mostly applicable to part B because the sample size of 90 in part A will not be adequate to produce an informative HIV efficacy analyses.

The MITT population will be used for this analysis. However, sensitivity analyses may be performed, limited to participants who received a certain number of doses or an analysis comparing each of the intervention arms to all placebo receiving participants, may be performed. The date of HIV infection diagnosis will be estimated as the midpoint between the last negative HIV test and the first confirmed positive HIV test date. Where a participant has a positive PCR and a negative or discordant rapid results on the same date, the date of infection is calculated as 14 days prior to this date. Alternatively, the single random-point method will be used in instances where we have missed visits(43). Participants who do not become HIV positive before their last study visit will be censored on the day of their last negative HIV test. Time at risk in days will be computed as the difference between the estimated date of HIV infection or date of censoring and the randomization date. The hazard ratio comparing CAP256V2LS + VRC07-523.LS vs placebo and a 95% confidence interval will be estimated using the univariable Cox proportional hazards model. Product efficacy calculated as 1 minus the hazard ratio and a 95% confidence interval will be presented. Secondly, Cox proportional hazards regression models will be used to estimate the hazard rate ratio and product efficacy along with a 95% confidence interval, controlling for baseline prognostic variables to improve precision.

In the event where the proportional hazards assumption is violated, a Poisson model with person-years of follow-up as an offset will be utilised. Furthermore, a sensitivity analyses will be conducted where the counterfactual placebo HIV incidence rate will be compared with the HIV incidence rate among those receiving CAP256V2LS and VRC07-523LS antibodies.

Acceptability of the SC injections among participants

The number and percentage of participants who discontinue the study product or prematurely withdraw from the study will be reported by study arm, with reasons for discontinuation summarised.

